5.6 Other Definitions

Baseline, Study Day and Event Duration are specifically defined as:

Baseline

Two baselines are defined:

- 1 Last assessment prior to first dose of study IMP on Day 0.
- 2 At 0 hours on Day 25 of the Confinement visit

Study Day

Study Day = (Date of event - first dose of study IMP) + 1.

Event Duration

Event Duration= (Date of resolution – Date of onset) + 1

6. Statistical Methods.

This statistical analysis plan specifies the requirements for the analysis and reporting of all data collected during the study.

All analyses and data reporting procedures will be undertaken using SAS® v9.4 in a Windows version 10 operating system environment.

The descriptive statistics produced will account for the nature and distribution of the data collected. For continuous variables (actual and percentage change from baseline), data will be presented as number (n), mean, median, standard deviation, and range. For discrete variables (Incidence, Response outcome) data will be presented as frequencies and proportions and the denominator will be the number of patients available.

Data collected from patients in each of the three cohorts (Part 1 AD, Part 1 PD, Part 2 PD) will be derived and summarised as described in section 5 and analysed according to the defined analysis population in section 4.

All comparisons of primary interest performed in Part 1 and Part 2 involve changes from baseline (Within treatment group). The null hypothesis throughout is that there is no difference between the Day 25 end of treatment and Pre-treatment baseline (H0. $X_{end}=X_{base}$, H1. $X_{end} \neq X_{base}$).

Between treatment groups comparisons are also possible (but of secondary interest due to the small sample size). Here the null hypothesis is that there is no difference between any of the treatment groups at the end of treatment (H0. Placebo= $X_{5mg}=X_{10mg}=X_{20mg}=X_{40mg}=X_{80mg}$, H1. Placebo $\neq X_{5mg} \neq X_{10mg} \neq X_{20mg} \neq X_{40mg} \neq X_{80mg}$).

6.1 Pharmacodynamic Endpoints

For the Part 1 AD and Part 1 PD cohorts, each variable measured in plasma and CSF will be analysed using an analysis of variance (ANOVA) model of the percentage changes from Baseline (between Baseline Day 0 Pre-dose 0h and Day 25 Pre-dose 0h). This will include Treatment group as a fixed effect and LSmeans (with 95% CI) for this effect will be presented (Within group).

Between group differences for 80mg vs Placebo will be assessed and presented (LSmeans +/- 95% CI) although results will be viewed cautiously given small control group samples size.

Then the percentage change from Baseline (Day 25 Pre-dose 0h) for each of the 6 hourly assessments will be analysed using a Repeated measured mixed model (RMMM) including Treatment group as a fixed effect, Time as the repeated effect and Subject as random term. Compound symmetry will be assumed for the covariance/correlation matrix. An overall average LSmean (with 95% CI) for the Treatment effect will be presented together with individual LSmean (with 95% CI) estimates for each hour. Treatment group differences will also be presented for the comparison between 80mg vs Placebo but the same caveat used given the control group subject sample size.

The maximum percentage change from Baseline (Day 25 Pre-dose 0h) over the 6 hours will also be analysed with an ANOVA model for both the Within treatment group and Between group (80mg vs Placebo) comparisons.

In the event of either model failing assumptions of normality or constant variance, a log transformed analysis of the actual values (*not percentage change*) will be substituted and the output estimates (means and 95% CIs) then back transformed by exponentiation to enable presentation of the ratio of values (%).

For the Part 2 PD cohort with 4 treatment dose groups (5, 10, 20, 40mg) the same analyses models will be employed. However, the data from the Part 1 PD patients will also be included (for those biomarker variables retained from Part 1 after evaluation at that stage) from both the Placebo and 80mg patient groups and combined with the Part 2 data. Within and Between group ANOVAs and RMMM model analyses will then be employed in a similar manner to Part 1. The Part 2 report of treatment group differences will include Placebo (from Part 1) versus each of the five active treatment groups, namely 5mg, 10mg, 20mg and 40mg from Part 2, and 80mg group from Part 1.

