3.1 Power and Sample Size Determination

This is an exploratory investigation of safety, tolerability, pharmacokinetics, pharmacodynamics and efficacy focusing on target engagement, pathway engagement and functional/cognitive measures. Ten patients per dose group will provide sufficient data to demonstrate within group changes for sAPP α and sAPP β to be of the order of 20-40% (see Table 1 below) and to characterise the PK of posiphen and support potential dose proportionality analyses.

Table 1: Sample Size Estimation

Biomarker	SD	Delta effect size	Within treatment group change	N/Group*
sAPP α	0.1695	0.3 to 2 SD	36%	9
sAPP β	0.1695	0.3 to 2 SD	24%	9

*With 80% power and 0.05 two tailed significance level

NB. Alpha-synuclein (aSYN) and in neurotransmitters provide valuable supporting information but changes are anticipated to be smaller and would require larger group sizes.

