5.2.1 Pharmacodynamic Endpoints

Pharmacodynamic endpoints are based on the assessments from protein levels in blood, plasma and CSF at the Baseline (0h Pre-dosing) and Day 25 (Confinement) visit (0h Pre-dosing, 1, 2, 3, 4, 5, 6h). Pre-dosing values at Baseline will be compared with Day 25 (Confinement) and derived as a percentage change from Baseline. The Percentage change from Day 25 0h pre-dose at 1, 2, 3, 4, 5 and 6h on Day 25 (Confinement) will also be derived and presented. The maximum percentage change determined over the 6h period may also be incorporated.

Table 3: Pharmacodynamic Endpoints

Pharmacodynamic measure	CSF	Plasma
Target Engagement		
aSYN monomers	X	
Aβ monomers:		
A β 40	X	X
A β 42	X	X
Soluble Amyloid Precursor Proteins:		
sAPP α	X	
sAPP β	X	
Tau Proteins:		
T-tau	X	X
P-tau	X	X
Pathway Engagement		
Axonal Transport:		
Neurofilament light (NfL)	X	X
Inflammatory factors:		
Complement 3	X	

	YKL40	X	
	sTREM2	X	
	GFAp	X	X
Synaptic factors:			
	SNAP25	X	
	Synaptotagmin	X	
	Neurogranin	X	
Control proteins:			
	Beta-trace protein	X	
Infective particles:			
	aSYN oligomers	X	
	A β oligomers	X	
Exosomes			X

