Once all patients in Part 2 have completed, the PK data and infective particle and exosomes data from all three cohorts will be made available and analysed separately.

Summaries will be presented by cohort and treatment, visit and time recorded as appropriate.

The table below summarises the schedule for presentation of each cohort's statistical report output:

Analysis	Cohort	Deliverables
1	Part 1 – PD Patients (14)	Disposition Tables and Listings Biomarker* Tables, Figures and Listings Functional/cognitive Tables, Figures and Listings Safety Tables and Listings
2	Part 1 – AD Patients (14)	Disposition Tables and Listings Biomarker* Tables, Figures and Listings Functional/cognitive Tables, Figures and Listings Safety Tables and Listings
On completion of Part 2:		
3	PD Patients (54) – including 14 PD patients from Part 1 and 40 PD patients from Part 2	Disposition Tables and Listings Biomarker* Tables, Figures and Listings Functional/cognitive Tables, Figures and Listings Safety Tables and Listings
4	PD Patients (50) – including ten 80mg PD patients from Part 1 and forty PD patients (5mg, 10mg, 20mg and 40mg) from Part 2 AD Patients (10) – 80mg patients from Part 1 All patients (68) from Part1 and Part 2	PK analyses Tables, Figures and Listings PK analyses Tables, Figures and Listings Infective Particles in CSF: Tables, Figures and Listings Exosomes in plasma: Tables, Figures and Listings

*Biomarker results (excluding infective particles and exosomes) from assays conducted in Part 1 will be evaluated by the Sponsor and will inform the choice of assays and subsequent output from Part 2

NB: Infective particles and exosomes biomarker data will not be presented until after the completion of Part 2

Detailed ‘table shells’ for Part 1 and Part 2 will be produced to accompany this SAP. These not only describe table layout but table numbering formats and also the level of accuracy (number of decimal places) to be described in each table.

The following described tables and figures will be included in the statistical report.

7.1 Study Status.

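### SAP 6.1 tests within-group biomarker change on arithmetic percent change, whose mean is above zero when nothing changes; the conditional switch to logs only partly repairs this, and the cost is mainly Part 1 power for modest falls.

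*SAP*

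**What the plan says.** SAP 6.1 sets the main biomarker analysis for both Part 1 cohorts: each plasma and CSF variable is "analysed using an analysis of variance (ANOVA) model of the percentage changes from Baseline", from Day 0 pre-dose to Day 25 pre-dose. Treatment group is a fixed effect, and each group's LSmean and 95% CI is the within-group result. Part 2 uses the same models with the Part 1 PD patients added.

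SAP 6 says of this comparison: "The null hypothesis throughout is that there is no difference between the Day 25 end of treatment and Pre-treatment baseline". SAP 2 says the same, and both rank between-group comparisons second because of the small samples.

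There is a safeguard. SAP 6.1 continues: "In the event of either model failing assumptions of normality or constant variance, a log transformed analysis of the actual values" replaces the percent analysis, and back-transformed results are shown as ratios. No diagnostic, threshold or decision-maker is named. Nor does it say whether the choice is made per biomarker or per report, or how the Day 0 value enters.

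The hourly mixed model is also on percent change, from Day 25 pre-dose. For the largest change in the six hours, SAP 5.2.1 is tentative ("The maximum percentage change determined over the 6h period may also be incorporated") while SAP 6.1 is firm: "The maximum percentage change from Baseline (Day 25 Pre-dose 0h) over the 6 hours will also be analysed with an ANOVA model". Neither section says whether maximum means the highest value or the largest change in either direction.

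**The concern.** The null concerns equality of two levels, but the test asks whether a mean percent change is zero. These are different questions. Take one patient going from 100 to 125 and another from 125 to 100. The group total is unchanged and the mean log ratio is zero, but the mean percent change is (25 - 20)/2 = +2.5%.

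Protocol 2 defines target engagement as a lowering of neurotoxic proteins, so the bias works against the effect sought. Part 1 is where a lost signal could matter most. SAP 7 says its biomarker results "will inform the choice of assays and subsequent output from Part 2", and with 14 patients an assumption check seldom rejects. The surplus of false rises applies to every analyte, including "Beta-trace protein", the one control protein in SAP Table 3, which Protocol 2.2 expects to stay level. Because the switch is far likelier with 54 patients than with 14, the same biomarker could be reported on different scales in analyses 1 and 3.

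**Working it through.** **The plan's own figure.** SAP Table 1 gives 9 per group. At a standardised change of 1.4, the two-group formula 2(1.960 + 0.842)²/1.4² = 15.70/1.96 = 8.01 rounds up to 9, so the figure reproduces. Its SD does not supply s: 0.1695 is the SD of the absolute sAPPα difference at 8 h (Protocol 6.2), not of a percent change or log ratio.

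**Direction of the bias.** Let r = Day 25/Day 0. If nothing changes and the two values are exchangeable, E[r] = E[1/r]. Since r + 1/r ≥ 2, E[r] ≥ 1, with equality only if no patient varies. This needs no distributional assumption.

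**Size of the bias.** If log r is normal with mean 0 and SD s, the mean percent change is exp(s²/2) - 1. At s=0.3, exp(0.045) - 1 = 4.6%; the other values are +2.0% (0.2), +8.3% (0.4) and +13.3% (0.5).

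**Plausible s.** The documents give none. The nearest evidence is the 0 h rows of the earlier study in Protocol 6.2 (n=4), using SD = SE × √4 and s = √ln(1 + (SD/mean ratio)²):

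| Row | SD of percent change | s if a positive entry is a fall | s if a rise |
|---|---|---|---|
| sAPPα 0 h | 0.2493 × 2 = 0.4986 | ratio 0.8309: 0.55 | ratio 1.1691: 0.41 |
| sAPPβ 0 h | 0.2227 × 2 = 0.4454 | ratio 0.8575: 0.49 | ratio 1.1425: 0.38 |

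This suggests about 0.38-0.55 from four patients. Two later rows, 8 h and 12 h among them, are lower: rows at 2, 6, 8 and 12 h imply 0.20-0.42 on the first reading. The same table shows the distortion: sAPPβ at 4 h has a mean difference of +0.0277 but a mean percent entry of -0.2181, opposite signs in the same patients.

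**Simulation.** Pooled-error t test for one 10-patient group; Part 1 as 10 + 4 (12 df), Part 2 as 4 + 5 × 10 (48 df); 20,000 runs per cell for the tail rates. Assumed trigger: Shapiro-Wilk p<0.05 on residuals, then the log ratio.

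No true change, false fall v false rise (nominal 2.5% each; simulation error up to about 0.3 points):

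| s | Part 1 with switch | Part 2 with switch | Switch fires, Part 1 / Part 2 |
|---|---|---|---|
| 0.2 | about 2 v 3% | 1.4 v 4.3% | 8 / 25% |
| 0.3 | 1.6 v 3.9% | 1.4 v 4.9% | 13 / 47% |
| 0.4 | 1.5 v 4.6% | 1.8 v 4.7% | 20 / 68% |
| 0.5 | 1.4 v 5.0% | 2.0 v 4.2% | 28 / 83% |

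Without any switch, Part 2 at s=0.4 would be about 0.3 v 7.7%, so the safeguard does real work there. Always on logs, each tail is 2.2-2.7%.

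Part 1 power, as written v always log, for both Table 1 effects:

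| s | 24% fall | 36% fall |
|---|---|---|
| 0.2 | 96 v 98% | 100 v 100% |
| 0.3 | 66 v 75% | 97 v 99% |
| 0.4 | 41 v 52% | 80 v 90% |
| 0.5 | not tabulated | 60 v 72% |

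Part 2, 24% fall: 99 v 99, 78 v 81 and 52 v 57% at s=0.2, 0.3 and 0.4; for a 36% fall about 1-2 points are lost at most. Adding a Brown-Forsythe trigger moves Part 1 power for a 24% fall only to 67 and 42% at s=0.3 and 0.4.

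**Maximum change.** With no effect and independent hourly errors (here s is the SD of log(hour h/0 h)), the largest absolute percent change with its sign has mean +7.3, +16.5 and +29.5% at s=0.2, 0.3 and 0.4. If maximum means the highest of six, logs do not help: the null mean is still +9 to +43% over s=0.1-0.4. The signed log ratio of largest size has null mean zero but is bimodal (under 1% of patients within 0.5s of zero), and it turns a uniform 20% fall into a 31-34% fall at s=0.2-0.4.

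**The case against.** The strongest reply is that this matters little. Protocol 6.5 treats the comparisons as descriptive. The summaries in SAP 6 include the median, which does not carry the bias. Total two-sided error in Part 1 is only about 5.0-6.4%. SAP 3.1 expects changes in sAPPα and sAPPβ "to be of the order of 20-40" per cent, and at the upper part of that range little power is lost unless s is about 0.4 or more. Both s and the Shapiro-Wilk trigger are assumptions. The SAP appendices (table shells, plot templates) were not available for this check and could define the maximum or the log output.

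All of that stands and limits the point. It does not remove it: the biased scale is the default for the SAP's own comparison of main interest, the safeguard is weakest in the smallest data set, and an unbiased scale costs almost nothing.

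A reader might infer more than the documents support:
- That the analysis would produce false evidence of lowering. It does the reverse.
- That the wrong assays would be dropped for Part 2. SAP 7 says only that Part 1 results inform the choice; no significance rule is stated.
- That between-group or functional results share the bias. The mean bias cancels between groups under no effect, and the functional scores use absolute change.

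**Conclusion.** The point holds as a change worth making, not as a flaw that invalidates the study. The positive mean under no change is certain wherever patients vary; its size depends on s. At s of 0.2 or less it is about 2% or less, and Part 1 loses about 2 points of power for a 24% fall. At s=0.3-0.4, Part 1 loses about 9-11 points for a 24% fall and 2-10 for a 36% fall. Part 2 loses at most about 5 and 2 points respectively, although the surplus of false rises remains in both parts.

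These figures rest on lognormal ratios, an assumed Shapiro-Wilk trigger at 0.05, and a log ratio to baseline after switching. No separate size was computed for the hourly model, which uses the same percent scale. The maximum-change test has a distinct problem: selecting the extreme hour distorts the within-group mean on either scale.

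**What to change.** In SAP 6.1:
- Prespecify log(Day 25 0h / Day 0 0h) as the ANOVA response for every biomarker in all cohorts, and log(hour h / Day 25 0h) in the hourly model.
- Report the geometric mean percent change, 100 × (exp(LSmean) - 1), with its 95% CI.
- Delete the conditional switch. Keep arithmetic percent change as a descriptive summary.
- Define maximum change and report it descriptively only. Do not replace it with a test on the signed largest log ratio.

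This takes SAP wording and programming, with no new data; SAP 6.4.2 already uses log analysis with back-transformed ratios for PK. The cost is about 3-5 points of between-group power against the 4 placebo patients (24% fall, s=0.3, as written v logs: 33 v 29% in Part 1, 37 v 32% in Part 2). Part of that is not a real loss, because as written the between-group lower tail under no effect is about 3% rather than 2.5%.

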2.2 Endpoints

SAFETY AND TOLERABILITY

- adverse events
- physical examinations
- vital signs
- 12-lead ECGs
- clinical laboratory values

PHARMACOKINETICS

PK parameters will minimally be determined, as data permit: Area under the curve (AUC), Cmax, Tmax, $t_{1/2}$, and CL.

Additionally, the following Exploratory Objectives will be evaluated:

TARGET ENGAGEMENT

Levels of neurotoxic proteins in blood, plasma and CSF

- aSYN and A β monomers and dimers, and infective oligomers
- A β 38,40,42
- soluble Amyloid Precursor Proteins: sAPP α and sAPP β
- T-tau and P-tau protein

PATHWAY ENGAGEMENT

Levels of proteins involved in the toxic cascade leading to nerve cell death in blood, plasma and CSF

- neurotransmitters
- neurotrophic factors
- Inflammatory factors
- Synaptic factors
- Control proteins that should not change

FUNCTIONAL/COGNITIVE MEASURES

PD: MMSE, WAIS-IV, MDS-UPDRS

AD: MMSE, WAIS-IV, ADAS-Cog 14, CDR

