7.2.1.1 Target Engagement - CSF

The target engagement CSF variables include: A β -40, A β -42, sAPP α , sAPP β , t-tau, p-tau-181 and a-SYN and are summarised in Tables 14.2.1.1.1 – 14.2.1.1.7.

Subsequently, the results from the Within group ANOVA model of the percentage changes from Baseline (between Baseline Day 0 Pre-dose 0h and Day 25 Pre-dose 0h) will be presented, together with Maximum Percentage Change over 6h (Day 25) from Baseline (Day 25 Pre dose 0h) (Model terms – Table 14.2.1.2; Model estimates – Table 14.2.1.3) and plotted as treatment estimates (Figures 14.2.1.1, Template 1).

Additionally, the percentage change from baseline (Day 25 Pre-dose 0h - Day 0 Pre-dose 0h) and the Maximum Percentage Change over 6h (Day 25) from Baseline (Day 25 Pre-dose 0h) will be analysed for Between group differences. This will initially involve analysing the change from baseline differences between the Placebo treatment groups in Part 1 and the 80mg patient groups from Part 1 in both the AD and PD cohorts, and subsequently the differences between the PD Placebo patients from Part 1 and the 5mg, 10mg, 20mg and 40mg Parkinson patient groups from Part 2; and repeating the PD Placebo versus PD 80mg

comparison (Model terms – Table 14.2.1.2; Model estimates – Table 14.2.1.3) and plotted as treatment estimate differences (Figures 14.2.1.2, Template 2).

Furthermore, the percentage change from Baseline (Day 25 Pre-dose 0h) for each of the 6 hourly assessments will be analysed using a Repeated measured mixed model (RMMM) and will be presented in Tables 14.2.1.4 and 14.2.1.5 for Within and Between treatment group model terms and estimates, respectively, together with corresponding plots (Figures 14.2.1.3, Templates 3 and 4, respectively).

On completion of the two Part 1 cohorts, the target engagement CSF biomarkers will be evaluated and this will inform a decision about which should be assayed and statistically analysed after Part 2 has been completed.

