7.2.1.2 Pathway engagement – CSF

The pathway engagement CSF variables include: NfL, GFAP, Complement C3, YKL40, sTREM2, SNAP25, Synaptotagmin, Neurogranin and Beta-trace protein and are summarised in Tables 14.2.2.1.1 – 14.2.2.1.9.

Subsequently, the results from the Within group ANOVA model of the percentage changes from Baseline (between Baseline Day 0 Pre-dose 0h and Day 25 Pre-dose 0h) will be presented, together with Maximum Percentage Change over 6h (Day 25) from Baseline (Day 25 Pre dose 0h) (Model terms – Table 14.2.2.2; Model estimates – Table 14.2.2.3) and plotted as treatment estimates (Figures 14.2.2.1, Template 1).

Additionally, the percentage change from baseline (Day 25 Pre-dose 0h - Day 0 Pre-dose 0h) and the Maximum Percentage Change over 6h (Day 25) from Baseline (Day 25 Pre dose 0h) will be analysed using a Between group ANOVA model. This will initially involve analysing the change from baseline differences between the Placebo treatment group from Part 1 and the 80mg Parkinson patient group from Part 1, and subsequently the differences between the Placebo from Part 1 and the 5mg, 10mg, 20mg and 40mg Parkinson patient groups from Part 2 (Model terms – Table 14.2.2.2; Model estimates – Table 14.2.2.3) and plotted as treatment estimate differences (Figure 14.2.2.2, Template 2).

Furthermore, the percentage change from Baseline (Day 25 Pre-dose 0h) for each of the 6 hourly assessments will be analysed using a Repeated measured mixed model (RMMM) and will be presented in Tables 14.2.2.4 and 14.2.2.5 for Within and Between treatment group model terms and estimates, respectively, together with corresponding plots (Figures 14.2.2.3, Templates 3 and 4, respectively).

On completion of the two Part 1 cohorts, the pathway engagement CSF biomarkers will be evaluated and this will inform a decision about which should be assayed and statistically analysed after Part 2 has been completed.

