7.2.2.1 Target Engagement - Plasma

The target engagement plasma variables include: A β -40, A β -42, t-tau and p-tau-181 and are summarised in Tables 14.2.3.1.1 – 14.2.3.1.4.

These variables are analysed as for the CSF variables:

Within group ANOVA model: Model terms – Table 14.2.3.2; Model estimates – Table 14.2.3.3) and plotted as treatment estimates (Figures 14.2.3.1, Template 1).

Between group ANOVA model: Model terms – Table 14.2.3.2; Model estimates – Table 14.2.3.3) and plotted as treatment estimate differences (Figure 14.2.3.2, Template 2).

Repeated measured mixed model (RMMM) – Within Group: Model terms – Table 14.2.3.4 and Model Estimates Table 14.2.3.5 and Between group also in Tables 14.2.3.4 and 14.2.3.5, respectively, together with corresponding plots (Figures 14.2.3.3, Templates 3 and 4, respectively).

On completion of the two Part 1 cohorts, the target engagement plasma biomarkers will be evaluated and this will inform a decision about which should be assayed and statistically analysed after Part 2 has been completed.

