7.2.2.2 Pathway Engagement - Plasma

The pathway engagement plasma variables include: NfL and GFAP and are summarised in Tables 14.2.4.1.1 – 14.2.4.1.2.

These variables are analysed as for the CSF variables:

Within group ANOVA model: Model terms – Table 14.2.4.2; Model estimates – Table 14.2.4.3) and plotted as treatment estimates (Figures 14.2.4.1, Template 1).

Between group ANOVA model: Model terms – Table 14.2.4.2; Model estimates – Table 14.2.4.3) and plotted as treatment estimate differences (Figure 14.2.4.2, Template 2).

Repeated measured mixed model (RMMM) – Within Group: Model terms – Table 14.2.4.4 and Model Estimates Table 14.2.4.5 and Between group also in Tables 14.2.4.4 and 14.2.4.5, respectively, together with corresponding plots (Figures 14.2.4.3, Templates 3 and 4, respectively).

On completion of the two Part 1 cohorts, the pathway engagement plasma biomarkers will be evaluated and this will inform a decision about which should be assayed and statistically analysed after Part 2 has been completed.

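### The within-group test of the maximum percentage change over 6 hours (SAP 6.1) is set up to reject without a drug effect, and the SAP text does not define the maximum

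*SAP*

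**What the plan says.** SAP 6.1 plans three analyses of each biomarker: an ANOVA of the percentage change from Day 0 pre-dose to Day 25 pre-dose, a repeated-measures model of the hourly changes from Day 25 0h, and a third: "The maximum percentage change from Baseline (Day 25 Pre-dose 0h) over the 6 hours will also be analysed with an ANOVA model". This third analysis is run "for both the Within treatment group and Between group (80mg vs Placebo) comparisons".

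SAP 7.2.1.1 puts it in the same model-term and estimate tables as the first ANOVA ("together with Maximum Percentage Change over 6h (Day 25) from Baseline (Day 25 Pre dose 0h") for seven CSF target variables. SAP 7.2.1.2 does the same for nine CSF pathway variables, ending with "sTREM2, SNAP25, Synaptotagmin, Neurogranin and Beta-trace protein". For the four plasma target variables, SAP 7.2.2.1 says "These variables are analysed as for the CSF variables", and SAP 7.2.2.2 repeats that for two more ("The pathway engagement plasma variables include: NfL and GFAP").

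SAP 5.2.1 is less firm: "The maximum percentage change determined over the 6h period may also be incorporated". None of these sections says whether the maximum is the largest rise, the largest fall or the largest absolute change, or whether the sign is kept. None gives a null value for it other than zero. SAP section 6 makes within-group change the main comparison, with a null of no change from pre-treatment.

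**The concern.** Each patient contributes six changes (hours 1 to 6), all measured against one Day 25 0h value. An extreme of six noisy quantities is generally not centred on zero when nothing is happening. Testing its group mean against zero then rejects because of how the endpoint is built, and more patients make this worse.

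The undefined direction matters because Section 2 of the protocol expects some markers to rise and others to fall, so the word alone does not settle the reading. The reading changes the error rate from close to nominal to near certainty.

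The SAP's caution about small numbers attaches to the placebo comparison, which is sound here, and not to the within-group result. A significant within-group maximum could therefore be read as a drug effect. SAP section 7 says Part 1 biomarker results will inform the Part 2 assays, although no section makes this test a selection rule. The variables include Beta-trace protein, a control of the kind the protocol lists as "Control proteins that should not change". It is exposed to the same artefact, so it cannot act as a control in this analysis.

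**Working it through.** The plan states no figure for this analysis, so there is none to reproduce.

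**Inputs from the documents.** Group sizes of 10 active and 4 placebo per Part 1 cohort (SAP 3.3). Six post-dose hours against one 0h value (SAP 5.2.1). Two-sided 5% level (SAP Table 1). LSmeans with 95% CI from an ANOVA with treatment as the fixed effect (SAP 6.1).

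**Assumed, because the documents do not give them.** Within-patient CV of 10, 15, 20 and 25%. AR(1) correlation of 0, 0.4 and 0.8 between hourly values. In the main setting the 0h value is as noisy as the others, there is no drift, and all six samples are present.

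**Hand check.** With independent normal noise of SD s, the largest of six changes from a shared baseline has mean +1.27s and SD 1.19s. The expected test statistic is about 1.27/1.19 × √10 = 3.4 for 10 patients and 1.27/1.19 × √4 = 2.1 for 4. The ANOVA has 10 + 4 − 2 = 12 error df, with critical value 2.18. Rejection should therefore be usual in the larger group and near even odds in the smaller. Simulation on the log scale at correlation 0 gives about 87% and 50%.

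**Simulation, no drug effect.** Log-normal values at 0 to 6h, percentage change from 0h, one-way ANOVA with pooled error, each LSmean tested against 0 and active against placebo, 10,000 trials per setting. False-positive rates in the main setting:

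| Reading of the maximum | 10 active | 4 placebo |
|---|---|---|
| Highest value | 71-89% | 31-48% |
| Largest fall | 67-86% | 34-52% |
| Largest absolute change, unsigned | about 100% | 93-100% |
| Largest absolute change, sign kept | 6-16% | 6-10% |

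With no effect, the mean highest change is +8 to +43% and the mean largest fall −7 to −24%. For scale, SAP 3.1 looks for within-group changes of 20-40% in sAPPα and sAPPβ. The active-versus-placebo comparison rejects 4-6% of the time here and 3-7% over all settings.

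**Sensitivity, 10-patient group:**

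| Setting | Highest | Largest fall |
|---|---|---|
| 0h noise SD × 1.5 | 37-67% | 26-57% |
| 0h noise SD × 2 | 24-49% | 13-37% |
| Compound-symmetric changes, r = 0.5 | 88-89% | 82-86% |
| r = 0.8 | 45-47% | 33-38% |
| r = 0.9 | 26-28% | 17-20% |
| Patient slopes, SD 0.5 noise SD per hour | 54-62% | 52-59% |
| Slope SD 1 | 24-37% | 29-38% |
| Slope SD 2 | 8-20% | 11-23% |
| Three of six samples | 38-55% | 31-47% |
| 0h noise × 2 and three samples | 14-28% | 7-17% |

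The unsigned reading stays at 97-100% except with patient slopes (92-100%, 55-95% and 15-64% for the three slope SDs). With log ratios in the main setting, the rates are 71-88% for highest and for fall, 100% unsigned and 5-6% signed. In the Part 2 layout (five groups of 10 plus 4 placebo, 54 − 6 = 48 df, 4,000 trials, main setting) they are 74-91%, 73-90%, 100% and 6-20%.

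**Expected count.** Variables per Part 1 cohort: 7 + 9 + 4 + 2 = 22. If none is affected by drug, the number flagged in the 10-patient group is:

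- highest or fall, main setting: 22 × 0.67 to 22 × 0.89, about 15 to 20
- highest or fall, r = 0.9: 22 × 0.17 to 22 × 0.28, about 4 to 6
- signed extreme, main setting: 22 × 0.06 to 22 × 0.16, about 1.3 to 3.5
- a true 5% test: 22 × 0.05 = 1.1

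**The case against.** The strongest reply has four parts.

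1. Protocol 6.5 calls the pharmacodynamic comparisons descriptive, and the zero null for the maximum is inferred from the within-group framework. Both are true. But the SAP still presents model terms, LSmeans and intervals for the maximum, and the label does not recentre them.
2. The largest change with its sign kept is a natural reading, and it is only mildly affected. This stands as a limit on size. Its excess comes from the skewness of percentage changes and nearly vanishes on the log scale. On the percentage scale its null mean was still about +1.5% to +22% at CV 10% and 25%.
3. The definition may sit in the table shells and plot templates (SAP Appendices 1-3), which were not available. That could answer the missing direction and sign. At best it would select the one mildly affected reading; it would not rescue the other three.
4. Practical harm is limited. Placebo and active estimates share the same tables, so a similar shift would show in placebo, and biomarkers are exploratory. This is fair and keeps the matter moderate. Four placebo patients are a weak visual check, however, and within-group change is the SAP's main comparison.

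It is also right that the count of 15 to 20 applies only to the highest and largest-fall readings, and that the rate for any one assay, Beta-trace included, depends on its own noise structure.

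**Conclusion.** The concern holds. As written, the within-group test of the maximum is not a valid test of no effect when the maximum means the highest value, the largest fall or the unsigned largest change. For these readings the main-setting false-positive rate in 10 patients runs from 67% to about 100% against a nominal 5%. Under every variant examined, the highest and fall readings exceed 5%, though only by a little (7-8%) in the most extreme. The signed reading gives 6-16% in the main setting. All rates rest on assumed hourly noise and correlation.

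The missing direction and sign is a real gap in the SAP text, subject to what the appendices contain. The Day 0 to Day 25 pre-dose ANOVA and the placebo comparison do not share the defect, and the primary safety and PK outcomes are unaffected. This should be fixed before the analysis, but it does not threaten the trial's main purpose.

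Three smaller points are editorial: *may* in SAP 5.2.1 against *will* in 6.1; a null in section 6 that is said to apply everywhere although the maximum and the hourly model use the second baseline in 5.6; and the unnamed baseline at the start of 7.2.

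**What to change.** - Define the maximum in the SAP text, with direction and sign, and reconcile SAP 5.2.1 with 6.1.
- Remove the within-group test and interval-based inference for the maximum from SAP 6.1, 7.2.1.1, 7.2.1.2, 7.2.2.1 and 7.2.2.2. Report it descriptively or against placebo only.
- Keep the Day 0 to Day 25 pre-dose ANOVA as the within-group analysis of 25-day change.
- Show the number of samples per patient beside the maximum. Protocol 9.4.2 lets CSF collections be skipped, and the mean null highest change is 8-43% with six samples but 6-29% with three.
- Label the hourly model and the maximum as acute effects within the dosing interval, confine the section 6 null to the Day 0-referenced analyses, and name the baseline in 7.2.

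The cost is SAP wording and the within-group rows for the maximum in Tables 14.2.1.2-3 and 14.2.2.2-3 and their plasma equivalents. No new data, assay or model is needed. The downside is that the remaining inferential comparison rests on 4 placebo patients, who in the Part 2 report come from Part 1 and were not randomised alongside the Part 2 dose groups.
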